9.11 Physician Training

All physicians included in this clinical trial are skilled in colorectal surgery. All treating physicians will have been trained on the use of the Colovac 2 Device prior to treating the first enrolled patient, as per internal SafeHeal training procedures and Investigator training plan specifications. The Site Initiation Visit will include a review of relevant procedural workflow and instructions for use for the SafeHeal Colovac 2 Colorectal Anastomosis Protection Device.

9.12 Patient Recruitment

Patients who meet eligibility criteria and agree to participate will be consented and enrolled. Upon regulatory and ethics committee approval of this protocol, patient enrollment will begin.

10.0 Patient Selection

10.1 Patient Selection Criteria for Eligibility

Inclusion Criteria:

Candidates for this study must meet ALL of the following criteria:

1. Adult patients (18 years of age or older)
2. Eligible to undergo open or minimally invasive sphincter-sparing low anterior resection with planned diverting loop ileostomy for malignancy, based on multidisciplinary team recommendations
3. Eastern Cooperative Oncology Group (ECOG) Performance Status ≤ 2
4. Willingness to comply with protocol-specific treatment and study visits and to sign a written Informed Consent Form

Exclusion Criteria:

Candidates will be excluded from the study if ANY of the following conditions apply:

Preoperative

1. History of left sided colitis
2. Known allergy to nickel or other components of the Colovac 2 System
3. Pregnant or nursing female subject

SAFE-2023 Colovac 2 Study Clinical Investigation Plan

4. Concomitant major surgical procedure in combination with Colorectal resection (i.e., hepatectomy)
5. Any serious or uncontrolled medical disorder that, in the opinion of the investigator, may increase the risk associated with study participation, impair the ability of the participant to undergo protocol described procedures or interfere with the interpretation of study results including, but not limited to:
 - a) Stage IV colorectal cancer unless curative intent R0 resection is planned AND there is no associated peritoneal disease
 - b) Immunodeficiency (CD4+ count < 500 CU MM)
 - c) Systemic steroid therapy within the past 6 months
 - d) Systemic infection at the time of surgery or requiring systemic antimicrobial therapy up to 1 week before surgery
 - e) Major surgical or interventional procedures within 30 days prior to this study or planned surgical or interventional procedures within 30 days of entry into this study
 - f) Diagnosis of bowel obstruction, bowel strangulation, peritonitis, bowel perforation, intraabdominal infection, ischemic bowel, carcinomatosis
 - g) Fecal incontinence, involvement of sphincter by the neoplastic disease or evidence of extensive local disease in the pelvis seen on pre-operative imaging
 - h) Severe malnutrition which is defined as at least 10% weight loss within 3 months prior to enrollment.
6. The subject is currently participating in another investigational drug or device study

Intraoperative

7. Anastomosis placement above the sacral promontory
8. Occurrence of any of the following during the colorectal surgery:
 - a) Blood loss (>750 cc)
 - b) Blood transfusion
 - c) Any new sign of ischemia
 - d) Positive air leak test
 - e) Inadequate bowel preparation
 - f) Anastomosis location greater than 15 cm from the anal verge
 - g) Other intra-operative risks that preclude the subject from undergoing the procedure with the investigational device

10.2 Expected enrollment rate / screening results

The clinical site is expected to enroll approximately 5 patients each month.

10.3 Screening Procedures

All patients considered for colorectal surgery and eligible for enrollment as determined by the study investigator should have the study explained to them, be given the study information sheet and informed consent form, and allowed time to consider whether or not they wish to take part in the study. The Investigator or a member of his/her staff should inform the patient about the study's

SAFE-2023 Colovac 2 Study Clinical Investigation Plan

purpose and risks/benefits. If the patient agrees to take part in the study and signs the consent form, the patient can then be screened by the investigator for study eligibility. If all inclusion criteria and no exclusion criteria are met, the patients should be enrolled in the study. Patients who give consent to take part in the study and subsequently do not meet the eligibility criteria will not be included in the intention to treat (ITT) population as detailed in 8.1.

10.4 Informed Consent

The Investigator or his/her staff will approach the patient to obtain written informed consent. The background of the proposed study and the potential benefits and risks of the study should be explained to the patient. Sufficient time will be given to the patient to understand the information provided and to ask any question related to the study and/or to the investigational device to the investigator and understand the answer provided.

The patient must sign the consent form prior to any evaluation specifically required for the study outside of routine practice. Failure to provide informed consent renders the patient ineligible for the study.

This form or a modification of it must have approval of the study site's Ethics Committee prior to obtaining patient consent. Patients may not be consented after receiving any medication that might alter their ability to comprehend the consent form (e.g., sedatives, narcotics, etc.).

The process of consent must be documented in the patient's hospital file.

11.0 Description of Treatments and Procedures

A summary of the study procedures by visit is provided in the tables below.

The pre-operative and intra-operative procedures are summarized below in Table 2.

Table 2: Pre-operative and Intra-operative Study Procedures

Procedure	Pre-Operative - 30 to -1 Days	Surgery Day 0
Informed Consent Signed	X	
Pregnancy Test for Female Subjects per hospital policies	X	
Screening/Preliminary Eligibility Determination	X	
Medical History, Concomitant Medications and Physical Examination	X	
ECOG performance status assessment	X	
Colorectal Resection Procedure (Index Surgery)		X
Surgery eCRF		X
Concomitant Medications		X

SAFE-2023 Colovac 2 Study Clinical Investigation Plan

Procedure	Pre-Operative - 30 to -1 Days	Surgery Day 0
Adverse Events		X
Colovac 2 Device Implantation Procedure		X
Implantation Usability Questionnaire		X
Colovac 2 Device Position X-ray		X

The procedures for Days 1 – 10 after surgery are summarized below in Table 3.

Table 3: Study Procedures for Days 1 - 10

Procedure	Hospital Day 1- 8 Daily	Hospital Day 9 (+3 days)	Hospital Day 10 (-1/+2 days)	If/when applicable
Device Position X-ray	X ¹	X ¹		
Daily Clinical Evaluation	X	X		
CRP	X ²	X ²	X ²	X ²
WBC	X ²	X ²	X ²	X ²
Daily Study Evaluation and Staff Ease of Device Use	X	X		
Trim Sheath (optional)	Day 2 only			
Double Contrast CT Scan of Anastomosis		X		
Concomitant Medications	X	X	X	X
AEs	X	X	X	X
Subject Tolerance and Ease of Use of Device			X	
Endoscopic Evaluation of Anastomosis (BBPS score) with still images			X ³	
Colovac 2 Retrieval			X	
Endoscopic Exam of Mucosa at the anchoring site Post-retrieval with video			X	
Evaluation of Anastomosis Post-retrieval			X	
Conversion to Ostomy				X
Retrieval eCRF			X	
Retrieval Usability Questionnaire			X	

¹ A baseline x-ray documenting device position will be obtained on Day 0 or Day 1. Additional x-rays documenting device position are required if device migration is suspected; otherwise, they are optional.

² Starting on Day 1 or 2, CRP and WBC will be tested every day during hospitalization.

³ If device is removed emergently due to peritonitis and endoscopic evaluation cannot be performed prior to device removal, the clinician will determine if the peritonitis is fecal related.

The procedures for the 1-month follow-up visit are summarized below in Table 4.

SAFE-2023 Colovac 2 Study
Clinical Investigation Plan

Table 4: Study Procedures for 1-Month Follow-up Visit

Procedure	1 Month (30±14 days)	If/when applicable
Endoscopic Exam of Mucosa at the anchoring site with video	X	X
CRP		X
WBC	X	X
Hemoglobin	X	X
Concomitant Medications	X	
AEs	X	X
Conversion to Ostomy		X
Ostomy Reversal		X

SAFE-2023 Colovac 2 Study Clinical Investigation Plan

11.1 Pre-operative Evaluation

Prior to the start of the study, the following steps will be completed and documented in the Case Report Form (CRF):

1. Confirmation that all inclusion criteria are passed, as defined in section 10.1.
2. Confirmation that no exclusion criteria are present, as defined in section 10.1.
3. Signed informed consent is obtained.
4. Within two weeks prior to the study unless otherwise noted, all patients enrolled into this study will undergo and have documented the medical history and ECOG evaluation, and physical examination. Additionally, concomitant medications will be documented.

11.2 Equipment

Each investigational site will provide standard colorectal surgery equipment for performing the Study and procedure.

SafeHeal will provide the following equipment:

- Colovac 2 Colorectal Anastomosis Protection Device pre-loaded inside its Introducer for each procedure, with back up
- SafeHeal Smartvac System
- SafeHeal canisters with tubing sets

Please refer to both the Instructions for Use for the Colovac 2 device and the Instructions for Use for the SafeHeal Vacuum System.

11.3 Study Procedures

D0 - Surgery and device implantation

The colorectal surgery is performed according to standard of care. After tumor resection and anastomosis creation, the device is implanted according to the procedure described in the Instructions for use.

Particular attention shall be paid to device positioning and to the Smartvac system connection.

D2 - Sheath cutting (optional)

At D2, the sheath may be cut according to the procedure described in the Instructions for use.

D0 – D10 (-1/+2) - Patient monitoring

The patient will be monitored daily until the device is retrieved on Day 10.

Patient Daily monitoring includes:

SAFE-2023 Colovac 2 Study Clinical Investigation Plan

- Fever
- Pulse
- Abdominal exam

Device daily monitoring should occur twice a day (T1 morning and T2 evening) and includes:

- Presence of fluid in the vacuum system collection reservoir
- Absence of blockage on the vacuum tube
- Length of the sheath protruding from the anus

If the stent migrates below the sacral promontory, documented by an X-ray or computed tomography, the physician should consider converting the patient to the standard of care ostomy within 24 hours.

Monitoring of C-reactive protein (CRP) and white blood cell (WBC) levels:

Starting on Day 1 or 2, CRP and WBC shall be tested every day during hospitalization.

Staff Ease of Use of Device:

The Staff member performing the Device daily monitoring will complete the Staff Ease of Use of the Device Questionnaire.

Day 9 (+3 days)

The day before device retrieval, a double contrast CT-scan shall be obtained to evaluate anastomosis integrity and healing. Images will be recorded and uploaded to a secure server, and read by an independent reviewer (CEC) to determine presence or absence of a leak and the description of the leak (if applicable).

Device retrieval D10 (-1/+2 days)

The device retrieval is composed of the following sequence:

1. Colonoscopy will be performed prior to the device retrieval, between the colon wall and the sheath, to assess visually the presence of feces (sealing function integrity of the Colovac 2 device) and the integrity of the anastomosis. The Boston Bowel Preparation Scale (BBPS, see Appendix 2) score will be assessed by an independent reviewer (CEC). Still images of the anastomosis will be captured during the procedure and the pseudonymized images should be sent on a secure platform for analysis, and anastomosis healing and signs of leak will be assessed by an independent reviewer (CEC).
2. Device retrieval - Please refer to the Instructions for use of the Colovac 2 Device for retrieval instructions.
3. Endoscopic evaluation after device retrieval

An endoscopic evaluation with video will be performed immediately after retrieval of the Colovac 2 Device to check for colonic wall injury at the anchoring site and to evaluate anastomotic integrity. The pseudonymized imaging should be uploaded on a secure platform for analysis. These will be

SAFE-2023 Colovac 2 Study Clinical Investigation Plan

analyzed by an independent reviewer (CEC) to determine vessel impact, with an assessment of mucosal appearance by grading bleeding, perforation and ulceration. If ulceration is present, percentage of ulceration will also be assessed.

After retrieval of the Colovac 2 Device, the anastomosis will be evaluated.

If an anastomotic defect is identified, treatment will be at the surgeon's discretion. Anastomotic defects/leaks may be treated with antibiotics only, and/or by percutaneous drainage, and/or surgically (revision of the anastomosis, repair of the anastomotic defect, stoma creation).

Handling of anastomotic complications during the implantation period

Any subject presenting with clinical signs suggestive of anastomotic leakage observed during the implantation period of the Colovac 2 Device will be treated as per standard clinical practice.

Subjects with clinical signs or symptoms of anastomotic leakage will undergo CT scan. Definitive treatment of anastomotic leakage will be per the treating surgeon's discretion and based on the severity of the clinical symptoms and radiological findings. Treatment may consist of antibiotics only, and/or percutaneous drainage, and/or reoperation.

11.4 Patient Follow-up

At 1-month post index surgery (± 14 days) an endoscopic evaluation with video should be performed to assess the healing of the colon mucosa at the anchoring site. The pseudonymized video should be uploaded on a secure platform for analysis. This video will be analyzed by an independent reviewer (CEC) to determine vessel impact, with an assessment of mucosal appearance by grading bleeding, perforation and ulceration. If ulceration is present, percentage of ulceration will also be assessed.

The 1-month visit will also collect any concomitant medications that have been added or removed and adverse events that have occurred since the Day 10 visit. Additionally, white blood count, hemoglobin and ostomy status will be collected.

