2.0 Protocol Synopsis

Title	SAFE (SafeHeal Anastomosis Evaluation)-2023 Study: A Study to Investigate the Performance and Safety of the Colovac 2 Colorectal Anastomosis Protection Device
Investigational Device	Colovac 2: Colorectal Anastomosis Protection Device following Low anterior resection (LAR) for colorectal cancer. The Colovac 2 System includes the Colovac 2 Colorectal Anastomosis Protection Device and the SafeHeal Vacuum Management Device (Smartvac). The Colovac 2 Device includes the Colovac 2 Implant (stent and sheath) and the Colovac 2 Introducer.
Study Design	This is a prospective, single arm study to evaluate the usability, and preliminary safety and effectiveness of the Colovac 2 - Colorectal Anastomosis Protection Device at Day 10 post-implantation. Subjects will be followed through 4 weeks after surgery to document the longer-term status of the anastomosis and any significant safety event post-discharge. All performance, safety and effectiveness endpoint analyses will include data collected through Day 10.
Sample Size	Up to 50 subjects
Proposed Indication for Use for the Study	The SafeHeal Colovac 2 Device is intended for use in patients requiring low anterior rectal anastomoses to limit stoma creation to only those patients requiring more time for anastomosis healing when the device is removed, allowing patients with a healed anastomosis to avoid stoma creation.
Sponsor	SafeHeal SAS [name]
Number of Sites	Up to 3 sites
Number of Subjects	Up to 50 Investigational (Colovac 2) Subjects
Study Treatment	Colovac 2 Device implantation after colorectal resection for colorectal cancer
Objectives	
The primary objective of the study is to assess the clinically significant migration rate of the device through post-procedure Day 10 when the device is removed.
 
The secondary objectives of the study are to assess the:
 
 • Preliminary safety and performance of the Colovac 2 System • Ease of use the Colovac 2 Colorectal Anastomosis Protection Device • Ease of use of the Colovac 2 Introducer and Implant and Vacuum Management Device
Primary Performance Endpoints at Day 10	The primary performance endpoint is the clinically significant migration rate of the Colovac 2 device during its 10-day implantation period.

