Pre-operative and Intra-operative Procedures

Procedure	Pre-Operative - 30 to -1 Days	Surgery Day 0
Informed Consent Signed	X	
Pregnancy Test for Female Subjects per hospital policies	X	
Screening/Preliminary Eligibility Determination	X	
Medical History, Concomitant Medications and Physical Examination	X	
ECOG Performance Status assessment	X	
Colorectal Resection Procedure (Index Surgery)		X
Surgery eCRF		X
Concomitant Medications	X	X
Adverse Events, Device Deficiency		X
Colovac 2 Device Implantation Procedure		X
Implantation Usability Questionnaire		X
Colovac 2 Device Position X-ray		X

Schedule of Study Procedures Day 1 - 10

Procedure	Hospital Day 1- 8 Daily	Hospital Day 9 (+3 days)	Hospital Day 10 (-1/+2 days)	If/when applicable
Device Position X-ray	X ¹	X ¹		
Daily Clinical Evaluation	X	X		
CRP	X ²	X ²	X ²	X ²
WBC	X ²	X ²	X ²	X ²
Daily Study Evaluation and Staff Ease of Device Use	X	X		
Trim Sheath (optional)	Day 2 only			
Double Contrast CT Scan of Anastomosis		X		
Concomitant Medications	X	X	X	X
AEs	X	X	X	X
Subject Tolerance and Ease of Use of Device			X	
Endoscopic Evaluation of Anastomosis (BBPS score) with still images			X ³	
Colovac 2 Retrieval			X	
Endoscopic Exam of Mucosa at the anchoring site Post-retrieval with video			X	
Evaluation of Anastomosis Post-retrieval			X	
Conversion to Ostomy				X
Retrieval eCRF			X	
Retrieval Usability Questionnaire			X	

¹ A baseline x-ray documenting device position will be obtained on Day 0 or Day 1. Additional x-rays documenting device position are required if device migration is suspected; otherwise, they are optional.

² Starting on Day 1 or 2, CRP and WBC will be tested every day during hospitalization.

³ If device is removed due to peritonitis and endoscopic evaluation cannot be performed prior to device removal because subject requires emergent surgery, the clinician will determine if the peritonitis is fecal related.

SAFE-2023 Colovac 2 Study
Clinical Investigation Plan

	Study Procedures for 1 Month Follow-up Visit		
	Procedure	1 Month (±14 days)	If/when applicable
	Endoscopic Exam of Mucosa at the anchoring site with video	X	X
	CRP		X
	WBC	X	X
	Hemoglobin	X	X
	Concomitant Medications	X	
	AEs	X	X
	Conversion to Ostomy		X
	Ostomy Reversal		X

SAFE-2023 Colovac 2 Study Clinical Investigation Plan

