9.9 Measurement Methodology

All patient clinical data will be collected on standardized case report forms.

Safety will be evaluated by determining the incidence of intra- and post-surgical complications and adverse events (including spontaneous patient reports) after 10 days and 4 weeks. Complications and adverse events will be recorded on the case report forms.

SAFE-2023 Colovac 2 Study Clinical Investigation Plan

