Grade I	Any deviation from the normal postoperative course without the need for pharmacological treatment or surgical, endoscopic and radiological interventions Allowed therapeutic regimens are: drugs as antiemetics, antipyretics, analgetics, diuretics and electrolytes and physiotherapy. This grade also includes wound infections opened at the bedside.
Grade II	Requiring pharmacological treatment with drugs other than such allowed for grade I complications. Blood transfusions and total parenteral nutrition also included.
Grade III	Requiring surgical, endoscopic or radiological intervention
- IIIa	Intervention not under general anesthesia
- IIIb	Intervention under general anesthesia
Grade IV	Life-threatening complication (including CNS complications)* requiring IC/ICU-management
- IVa	Single organ dysfunction (including dialysis
- IVb	Multi organ dysfunction
Grade V	Death of a patient

*brain hemorrhage, ischemic stroke, subarachnoidal bleeding, but excluding transient ischemic attacks (TIA),
Intermediate care: IC; ICU: Intensive care unit.

The following information will also be collected:

- Seriousness using the SAE definition above
- Action taken
- Date of resolution
- Outcome

³ Dindo D, Demartines N, Clavien PA. Classification of surgical complications: a new proposal with evaluation in a cohort of 6336 patients and results of a survey. Ann Surg. 2004;240(2):205-213.
doi:10.1097/01.sla.0000133083.54934.ae

SAFE-2023 Colovac 2 Study Clinical Investigation Plan

All AEs (regardless of relationship) must be collected from the time the informed consent is signed through the last follow-up visit. All AEs must be recorded on the appropriate AE eCRF and in source documents.

All adverse events will be followed until the event is resolved or stabilized and/or deemed permanent, or until the subject's participation in the study ends.

If the AE meets the criteria for an SAE, the investigator must complete the AE form in the EDC system, as soon as possible, but no later than 3 days of knowledge of the event.

In addition, anastomotic leaks will be graded according to the ISREC grading system that classifies ALs into one of three grades based on severity and required treatment (see appendix 3).

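### The 1-month visit may fall as early as Day 16, 12 days short of the stated 4-week follow-up, with its healing endoscopy 4 to 35 days after in-window device removal

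*Combined protocol and SAP*

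**What the plan says.** On the length of follow-up, the synopsis (2.0, Study Design) states: "Subjects will be followed through 4 weeks after surgery to document the longer-term status of the anastomosis and any significant safety event post-discharge". Section 9.9 agrees, evaluating complications and "adverse events (including spontaneous patient reports) after 10 days and 4 weeks".

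On the visit that delivers it, section 11.4 reads: "At 1-month post index surgery (± 14 days) an endoscopic evaluation with video should be performed". The stated aim is a check on mucosal healing where the device sat. Table 4 in section 11.0 heads the column "1 Month (30±14 days"; the synopsis schedule has "1 Month (±14 days" without a nominal day. The visit also collects adverse events, concomitant medication, white cell count, hemoglobin and ostomy status. No later visit or contact is scheduled. Table 4 has an if/when-applicable column, but nothing in it guarantees an assessment at Day 28.

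On retrieval, section 11.3 and Table 3 place device removal at Day 10 with a window of −1/+2 days. No minimum interval between removal and the 1-month endoscopy is given.

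On the end of adverse event collection, section 14.2 says events "must be collected from the time the informed consent is signed through the last follow-up visit". Section 16.1.2 instead continues documentation for 7 days (non-serious) or 30 days (serious) after the last day of participation.

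The synopsis also restricts all endpoint analyses to data through Day 10.

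**The concern.** The stated follow-up and the visit window do not fit together. A site can follow the schedule exactly and still end a subject's scheduled observation well before 4 weeks. The two rules for ending adverse event collection differ, and only one of them takes serious events past Day 28 for such a subject.

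The endoscopy raises a separate point. Its purpose is to see how the mucosa has healed where the device was anchored, so the natural clock starts at removal. The window is counted from surgery, and removal itself has a window, so the time available for healing varies widely between subjects whose results carry the same label. At the short end, the examination comes only days after the endoscopy that section 11.3 already requires immediately after retrieval, with the same grading of bleeding, perforation and ulceration.

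At stake is the descriptive picture after Day 10 in a single-arm study of up to 50 subjects. Section 6.3 says a new benefit-risk assessment will be made from these results. The risk lists in the synopsis and section 6.2 name colonic stenosis, ulceration and bleeding among events that may arise during or after the implant period. Unequal observation after removal could undercount them.

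**Working it through.** Day 0 is the index surgery.

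**Inputs**
- Nominal visit Day 30, window ±14 days (Table 4; ±14 also in 11.4 and the synopsis schedule)
- Stated follow-up of 4 weeks = 28 days (synopsis; 9.9)
- Retrieval on Day 10, −1/+2 (11.3; Table 3), i.e. Day 9 to Day 12
- End of adverse event collection: last visit (14.2), or last day of participation + 7 days non-serious and + 30 days serious (16.1.2)

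**1. The plan's own window**
- Earliest: 30 − 14 = Day 16
- Latest: 30 + 14 = Day 44
- Permitted days: 44 − 16 + 1 = 29

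**2. Shortfall against 4 weeks**
- Largest shortfall: 28 − 16 = 12 days
- Permitted days before Day 28 (Days 16 to 27): 12, and 12/29 = 41%

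**3. Adverse events for a subject who leaves on Day 16**
- Under 14.2: all events to Day 16
- Under 16.1.2, non-serious: 16 + 7 = Day 23, which is 28 − 23 = 5 days short
- Under 16.1.2, serious: 16 + 30 = Day 46, past Day 28

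**4. Removal to healing endoscopy, with in-window retrieval**
- Shortest: 16 − 12 = 4 days
- Nominal: 30 − 10 = 20 days
- Longest: 44 − 9 = 35 days
- Any visit on Day 16: 16 − 12 = 4 to 16 − 9 = 7 days

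Removal before Day 9, which the plan foresees for events such as peritonitis (Table 3, footnote 3), would lengthen the upper end.

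**5. Sensitivity to the meaning of 1 month** (only Table 4 gives the day)

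| 1 month read as | Window | Largest shortfall | Removal to endoscopy |
|---|---|---|---|
| 28 days | Day 14–42 | 14 days | 2–33 days |
| 30 days (Table 4) | Day 16–44 | 12 days | 4–35 days |
| 31 days | Day 17–45 | 11 days | 5–36 days |

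No reading removes the gap.

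**6. With an early limit at Day 28 and the upper limit kept at Day 44**
- Permitted days: 44 − 28 + 1 = 17
- Shortest interval after in-window retrieval: 28 − 12 = 16 days; the longest stays 35

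**The case against.** The other side has several fair points.

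- **Serious events.** A reader might infer that the plan drops serious events between Day 16 and Day 28. Section 16.1.2 does not support that: its 30-day limb reaches Day 46 for a Day 16 exit, and serious events are the category closest to the significant safety events the synopsis wants documented. This stands, but only under 16.1.2. Section 14.2 stops at the visit, so the two sections conflict.
- **Endpoints.** A reader might think the study's endpoints are compromised. They are not. All endpoint analyses use data through Day 10, and the mucosal endpoint in 9.8 rests on the endoscopy done right after retrieval. This stands in full.
- **Pooling.** It is tempting to say that mixing 4-day and 35-day readings makes the healing result uninterpretable. The documents describe no such pooled analysis. Section 13.0 defers to a statistical analysis plan and promises patient listings and adverse event timing relative to the procedure. The interval should be derivable from recorded dates. The documents also give no healing-time figure, so how strongly the result depends on the interval is a plausible assumption, not a documented fact. What stands is narrower: nothing in the text available says the interval will be reported.
- **Worst case.** Four days needs the latest in-window retrieval and the earliest visit in the same subject; the nominal interval is 20 days. This stands.
- **The remedy is partial.** A Day 28 limit still leaves 16 to 35 days after removal, counted from surgery. That is true, and it is why the interval should be reported as well.

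**Conclusion.** The inconsistency is real and follows from the current text. A compliant subject can finish up to 12 days before the stated 4 weeks for ostomy and anastomosis status, laboratory tests and endoscopy. Non-serious events end at Day 16 or Day 23, depending on which section is followed. Serious events are covered past Day 28 under 16.1.2 but not under 14.2. The healing endoscopy can fall 4 to 35 days after in-window removal under a single 1-month label.

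The effect is confined to the descriptive 4-week safety and mucosal-healing results. The documents do not support saying that 4-week safety follow-up fails altogether, or that early visits will be common; the figures show what is permitted, not what sites will do. They rest on Table 4's Day 30 and on retrieval within its window, and the shortfall survives reading a month as 28 or 31 days. The change is worth making because following the plan exactly would not guarantee what the plan says it delivers.

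**What to change.** 1. **Reconcile the window with the 4 weeks.** Set the early limit no earlier than Day 28 in 11.4, Table 4 and the synopsis schedule, and keep Day 44 as the upper limit. Day 28 is the protocol's own figure. If sites need the wider window, restate in the synopsis and 9.9 the follow-up that is actually delivered.
2. **Report the interval.** Present the 1-month mucosal result with the days from device removal to endoscopy, from dates already collected.
3. **Reconcile 14.2 with 16.1.2** on when adverse event collection ends, separately for serious and non-serious events.
4. **Subjects already seen.** Section 9.2 records enrollment from July 2024, so some may have been seen before Day 28. Report their actual follow-up time. A telephone check of adverse events and ostomy status is optional.

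The cost is amendment wording and one derived variable; future subjects need no extra visit or procedure. The downside is a narrower scheduling window, 17 permitted days instead of 29, and possibly more out-of-window visits to handle as deviations.
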